#### Urogenital infections in different female populations at risk in Rwanda

In the context of the above-mentioned SRH studies, RU has worked with high risk women (most of whom were sex workers), female clients of public voluntary HIV counselling and testing (VCT) sites, HIV-positive women before and during antiretroviral therapy (ART) at public clinics, and women in the general population. The following table, containing data from these studies, shows that all urogenital infections are common in these populations.

Prevalence (%)	KHIS high risk women 	KHIS female VCT clients 	VBMS HIV-neg high risk 	VBMS HIV-pos women 	SEARCH HIV-pos  Pre-ART/on ART
Year of the Study	2006-2009	2007-2009	2010-2012	2010-2012	2007-2010
HIV	24	13	04	1004	1004
HSV-2	60	43	47	83	86 / 92
High risk HPV	37	ND	ND	ND	38 / 53
Syphilis	7	ND	7	20	3 / 4
Neisseria gonorrhoeae	12	ND	7	13	14 / 7
Chlamydia trachomatis	5	ND	10	0	5/5
Trichomonas vaginalis	17	ND	10	10	ND
Bacterial vaginosis (Nugent 7-10)	40	ND	44	36	ND
Intermediate microbiota (Nugent 4-6)	15	ND	19	21	ND
Vaginal candidiasis	7	ND	10	13	ND
Urinary tract infection	ND	ND	23	23	ND
Uses modern method of contraception excl. condoms	19	14	70	54	40
Never HIV tested before	35	25	ND	NA	NA

KHIS [1-4], VBMS [5-7] and SEARCH [8] are study acronyms; ND=not done; NA=not applicable.

1. Female sex workers or other women with multiple partners.

2. Clients of public VCT centres in Kigali city; not selected by risk behaviour.

3. HIV positive women receiving care at a public HIV clinic in Kigali; not selected by risk behaviour.

4. By study design; only HIV-negative or HIV-positive women included.

The viral sexually transmitted infections (STIs) herpes simplex virus type 2 (HSV-2) and human papillomavirus (HPV) were the most common, followed by the various vaginal infections (bacterial vaginosis (BV) and intermediate microbiota, *Trichomonas vaginalis* (TV), and vaginal candidiasis) and urinary tract infections (UTIs). The bacterial STIs *Neisseria gonorrhoeae* (NG), *Chlamydia trachomatis* (CT), and syphilis were less common, but higher prevalence rates were measured in a currently ongoing study in high risk women at RU: 12% for NG and 20% for CT (unpublished data).

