#### Point of care (POC) diagnostic tests

One way to improve urogenital infection care in women is to introduce POC diagnostic testing (21). Validated POC tests for HIV (22), syphilis (23), UTIs and pregnancy have been available for many years and are well-integrated into public clinics, including in resource poor settings. Most POC tests for HIV and syphilis are immunochromatographic assays that detect pathogen antigens or antibodies in small amounts of blood (a finger prick is sufficient). UTI and pregnancy POC tests are dipsticks that are submerged in a urine sample. UTI dipsticks detect leukocytes (among other analytes), and pregnancy dipsticks detect the human chorionic gonadotropin (hCG) hormone.

More recently, POC tests were developed for TV and CT/NG. The OSOM TV POC test (Sekisui Diagnostics, San Diego, CA, USA) is an immunochromatographic dipstick test that detects TV antigens in vaginal swab eluent; it was found to be 77% sensitive and 99% specific compared to TV polymerase chain reaction (PCR) in a study in Brazil and South Africa (24). This means that 24% of cases were misdiagnosed (23% false-negative and 1% false-positive). In Rwanda, TV is currently diagnosed by symptoms only, and a recent study in India found that 86% of patients with PCR-proven TV were misdiagnosed on the basis of symptoms alone (25). The TV OSOM POCT is therefore a significant improvement over the current situation.

The development of a POC enzyme immunoassay for NG and CT has proved difficult: all tests that were developed and evaluated thus far had poor sensitivity (26, 27). However, a POC real-time molecular test (detecting NG and CT DNA) is now available: the GeneXpert test (Cepheid, Sunnyvale, CA, USA) (28). While the GeneXpert test is highly sensitive and specific for NG and CT, it does not fulfil all ASSURED (affordable, sensitive, specific, user-friendly, rapid and robust, equipment-free and deliverable to end users) criteria (27): for example, testing requires a machine and about 90 minutes per sample. Research on CT/NG POC tests that do fulfil the ASSURED criteria is ongoing. Meanwhile, the GeneXpert platform is a significant improvement over syndromic management (the abovementioned recent study in India found that 80% of women with PCR-proven CT and 50% of women with PCR-proven NG were misdiagnosed on the basis of symptoms alone; 25) and traditional PCR platforms, and is being rolled out in select specialised centres across Africa.

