BV is usually diagnosed empirically (based on self-reported symptoms) in public primary care clinics, by Amsel criteria in specialised clinics (29), and by Gram stain Nugent scoring in specialised referral clinics and research settings (30). The Amsel criteria and Nugent scoring require skilled microscopists, who are usually not available in resource-poor settings. In the last decade, entire bacterial communities in the vagina have been characterised in detail (referred to as 'vaginal microbiota') using novel molecular testing techniques. We now know that vaginal microbiota that are dominated by Lactobacillus species are healthy and that BV is a polybacterial dysbiosis: lactobacilli are no longer dominant and the bacterial diversity in the vagina increases (31). Intermediate microbiota might represent a transition to or from dysbiosis. RU studies showed that increasing bacterial diversity in the vagina is not associated with the presence of urogenital symptoms, but is associated with increasing prevalence of HIV, HSV-2, HPV, bacterial STIs, and UTIs (15). While more research is needed to investigate these relationships, we believe that the currently available evidence is sufficient to justify treatment of both symptomatic and asymptomatic BV. Our research has also shown that the vaginal pH (which can be easily measured by putting some vaginal fluid on litmus paper in the vaginal pH range) is strongly correlated with the types of bacteria that are present in the vagina. Lactobacilli are very strong lactic acid producers and cause the vagina to be acidic (low pH, typically 3.6-4.1) whereas the bacteria associated with BV produce no or less lactic acid and cause the vaginal pH to be higher (31). Based on data from our previous studies in similar populations, we have chosen to treat all women with a vaginal pH  $\ge$  5.0 regardless of symptoms for BV. This cut-off achieved a sensitivity of 71% and a specificity of 76% when a Nugent score of 7-10 was used as the gold-standard for BV diagnosis in unpublished studies conducted at RU. In addition,

women with a lower vaginal pH will be treated when they have severe symptoms consistent with BV to minimise false-negative diagnoses. In comparison, a South African study in 2012 showed that the sensitivity of using symptoms alone to diagnose BV was only 10% (32).

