
 
Implement improved urogenital infection care services and monitor and evaluate these services
 
	
 
M&E indicators, such as         
 
Inputs: Procurement requirements;
 
Activities/outputs: N scored, diagnostic te treated, and referral activity; time spent a
 
Outcomes/impacts: I services (from client
 
 
 
	
 
M&E indicators, such as:
 
Inputs: Procurement experiences, infrastructure/training requirements;
 
Activities/outputs: Numbers of clients counselled and risk scored, diagnostic tests conducted, infections diagnosed and treated, and referrals made; staff time required for each activity; time spent at the clinic for each client trajectory;
 
Outcomes/impacts: Improvements of access to and quality of services (from client satisfaction survey, staff interviews).
 
		
Secondary objectives	Secondary endpoints			

 
Compare performance of syndromic management, POC testing after risk scoring, and POC testing of everyone for the diagnosis of NG, CT, TV, and BV.
 
	
 
Sensitivity, specificity, P         
 
Syndromic vs POC te
 
Syndromic vs risk scc
 
Risk scoring followed everyone (NG, CT)
 
If funding permits, al molecular testing of
 
 
 
	
 
Sensitivity, specificity, PPV, and NPV for:
 
Syndromic vs POC testing of everyone (NG, CT, TV and BV)
 
Syndromic vs risk scoring followed by POC testing (NG, CT)
 
Risk scoring followed by POC testing vs POC testing of everyone (NG, CT)
 
If funding permits, also all of the above vs gold standard molecular testing of everyone (NG, CT, TV, BV, and UTI)
 
		

 
Compare cost- effectiveness of all of the above
 
	
 
Cost effectiveness parar
 
Total costs for each of
 
Costs per correctly and
 
Total cost per disabilities
 
	
 
Cost effectiveness parameters, such as:
 
Total costs for each diagnostic algorithm
 
Costs per correctly and incorrectly managed infection
 
Total cost per disability adjusted life year (DALY) averted
 
		
Qualitative research objectives         Qualitative research endpoint		Qualitative research endpoints		
3a.Obtain stakeholder opinior	s about potential	
 
Consensus, majority and minority
 
		

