#### 4.3 Sample size

The primary objective is descriptive. Formal sample size calculations were therefore not performed. We estimated to be able to see 500-700 women in one year with the funding we received from EDCTP. However, our estimate may have been conservative, in which case the sample size may be increased to up to 1,000 women. Based on prevalence data from recent RU studies in the same high risk population, if we see 500 clients (assuming that they do not opt out of any services offered), we expect to diagnose 100 cases of HIV, 35 cases of syphilis, 60 cases of NG, 75 cases of CT, 75 cases of TV, 175 cases of BV, 50 cases of vaginal candidiasis, and 115 cases of UTI.

Data for the qualitative research objectives will be gathered at two workshops with stakeholders: one to be held before initiation of the study and one after completion of the study. In addition, IDIs will be done with clinicians, programme implementers and policymakers. The number of IDIs to be held will be governed by data saturation: no new interviews will be done when they no longer generate new information. We expect to conduct approximately 10 IDIs.

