5.3 Comparisons syndromic management vs. WISH procedures vs. gold standard testing In this section, all hypothetical syndromic management (under WHO guidelines) individual algorithms and presumed treatments of STIs will be compared to the POCT results as performed during the WISH study, and to the gold standard results. For each outcome, sensitivity, specificity, positive predictive value (PPV) and negative predictive value (NPV) will be reported (see next page).

Procedure 1	Procedure 2	N pos/pos	N pos/neg	N neg/pos	N neg/neg	OR (95% CI) ¹	Sens. ²	Spec. ²	PPV ²	NPV ²
	(reference)	(= TP)	(= FP)	(= FN)	(= TN)	Fisher's p	(%)	(%)	(%)	(%)
Syndromic (WHO)	WISH procedures									
Any VDS (with or without LAP,	CT/NG (after RS) ³ by POCT, TV/BV						_			
typical or not for candidiasis)	by POCT, or treated for candidiasis								 	
Any VDS (with or without LAP,	CT/NG (after RS) ³ by POCT, TV/BV									
typical or not for candidiasis)	by POCT								 	
Any VDS (with or without LAP,	CT/NG (after RS) ³ by POCT									
typical or not for candidiasis)									L	
Any VDS (with or without LAP,	CT (after RS) ³ by POCT						_			
typical or not for candidiasis)									L	
Any VDS (with or without LAP,	NG (after RS) ³ by POCT						_			
typical or not for candidiasis)									 	
Any VDS (with or without LAP,	TV/BV by POCT						_			
typical or not for candidiasis)									 	
VDS (with or without LAP, typical	Treated for candidiasis									
for candidiasis)									 	
PID (with or without VDS, after	CT/NG (after RS) ³ by POCT, TV/BV									
LAP)	by POCT								Ļ	
PID (with or without VDS, after	CT/NG (after RS) ³ by POCT									
LAP)									Ļ	
PID (with or without VDS, after	TV/BV by POCT						_			
LAP)									Ļ	
GUD	Syphilis algorithm (after RS) ⁴						-			
									Ļ	
Would have received treatment	CT/NG (after RS) ³ by POCT									
for CT/NG ⁵									Ļ	
Would have received treatment	TV/BV by POCT								ł	
for TV/BV ⁵									ł	

Procedure 1	Procedure 2	N pos/pos	N pos/neg	N neg/pos	N neg/neg	OR (95% CI) ¹	Sens. ²	Spec. ²	PPV ²	NPV ²
	(reference)	(= TP)	(= FP)	(= FN)	(= TN)	Fisher's p				
Syndromic (WHO)	Gold standard	-		_				-		-
Any VDS (with or without LAP,	CT/NG (on everyone) by POCT, or									
typical or not for candidiasis)	TV/BV ⁶ /CA by qPCR									
Any VDS (with or without LAP,	CT/NG (on everyone) by POCT, or									
typical or not for candidiasis)	TV/BV ⁶ by qPCR									

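### SAP 5.3 reports agreement with the TV/BV point-of-care tests as sensitivity and specificity of syndromic management, although vaginal pH is too inaccurate to be the reference

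*Protocol*

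**What the plan says.** The secondary endpoint in protocol 4.2 is sensitivity, specificity, PPV and NPV for "Syndromic vs POC testing of everyone (NG, CT, TV and BV". Molecular comparison is conditional there: "If funding permits, also all of the above vs gold standard" molecular testing. The protocol is ambiguous about the reference, because its synopsis lists POCT of everyone as a strategy with its own sensitivity and specificity.

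SAP 5.3 is explicit. Syndromic algorithms "will be compared to the POCT results as performed during the WISH study, and to the gold standard results". In the table the second procedure is headed as the reference, the four cells are labelled TP, FP, FN and TN, and the four accuracy measures are computed from them. Where the comparator is WISH procedures, that reference includes TV and/or BV by POCT.

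The accuracy of those tests is given in protocol 3.1. For pH of 5.0 or more: "This cut-off achieved a sensitivity of 71% and a specificity of 76% when a Nugent score of 7-10 was used as the gold-standard". For OSOM: "it was found to be 77% sensitive and 99% specific compared to TV polymerase chain reaction (PCR").

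The SAP also holds a better reference. Section 4.2 reports that qPCR for TV and a qPCR vaginal health score for BV were performed on Main Visit samples.

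**The concern.** A test that misses 29% of BV cases and flags 24% of women without BV cannot define who is a true or false positive. If a woman has BV, reports symptoms and has a low pH, the table counts her as a syndromic false positive. If she has no BV, no symptoms and a raised pH, she counts as a syndromic false negative. In both cases the syndromic rule was right.

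A reader who sees a column headed sensitivity will take it as accuracy. Where a qPCR row also exists, one rule gets two different sensitivities and nothing marks the first as agreement. Where none exists, the agreement figure is the only one printed. These results go to a stakeholder workshop on urogenital care in Rwanda (protocol 7).

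**Working it through.** **Rows affected.** Counting the blocks of SAP 5.3 that compare syndromic management with WISH procedures:
- TV and/or BV by POCT is the sole reference in 8 rows (3 WHO, 5 Rwandan). Seven use TV/BV combined; one, asymptomatic sex workers, uses TV only.
- It is part of a wider composite in 7 more (3 WHO, 4 Rwandan).

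**Inputs.**
- pH: sensitivity 0.71, specificity 0.76. This is unpublished and given without counts, so it can be quoted but not reproduced.
- OSOM: sensitivity 0.77, specificity 0.99.
- Prevalence: protocol 4.3 expects "75 cases of TV, 175 cases of BV" among 500 women, so 75/500 = 15% and 175/500 = 35%. The protocol 3.1 table row "Bacterial vaginosis (Nugent 7-10") gives 36%, 40% and 44%; TV there is 10-17%. I use BV 35-44% and TV 10-17%.

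**A flawless BV rule scored against pH.** Its apparent sensitivity is the PPV of pH, and its apparent specificity is the NPV of pH. At prevalence p:
- apparent sensitivity = 0.71p / [0.71p + 0.24(1-p)]
- apparent specificity = 0.76(1-p) / [0.76(1-p) + 0.29p]

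| BV prevalence | Apparent sensitivity | Apparent specificity |
|---|---|---|
| 35% | 0.2485/0.4045 = 61.4% | 0.4940/0.5955 = 83.0% |
| 40% | 0.2840/0.4280 = 66.4% | 0.4560/0.5720 = 79.7% |
| 44% | 0.3124/0.4468 = 69.9% | 0.4256/0.5532 = 76.9% |

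At 35% prevalence and N = 705, pH gives about 110 false positives and 72 false negatives. A rule that is right in those 182 women (26%) is scored wrong.

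**A flawless TV rule scored against OSOM.** At 15% TV: sensitivity 0.1155/0.1240 = 93.1%, specificity 0.8415/0.8760 = 96.1%. About 30 of 705 women (4.3%) are misclassified.

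**The combined TV/BV reference.** I read it as either test positive and assume that the infections, and the errors of the two tests, are independent. At BV 40% and TV 15%:
- Neither infection: 0.60 × 0.85 = 0.51. Both tests negative: 0.51 × 0.76 × 0.99 = 0.384. False positive: 0.126.
- At least one infection: 0.49. Both tests negative: 0.34 × 0.29 × 0.99 + 0.09 × 0.76 × 0.23 + 0.06 × 0.29 × 0.23 = 0.117. True positive: 0.373.
- Apparent sensitivity 0.373/(0.373 + 0.126) = 74.7%; apparent specificity 0.384/(0.384 + 0.117) = 76.6%.

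Over BV 35-44% and TV 10-17% the ranges are 68-78% and 73-81%.

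**A real syndromic rule.** With errors independent of pH errors given true status:
- apparent sensitivity = [Se × TP + (1-Sp) × FP] / (TP + FP)
- apparent specificity = [(1-Se) × FN + Sp × TN] / (FN + TN)

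A rule that is truly 80%/80% would show 56.9%/69.8% at 35% prevalence. But the protocol cites a South African study in which "the sensitivity of using symptoms alone to diagnose BV was only 10" per cent. No specificity is given, so I assume 80-95%. Then:
- At 35% prevalence and specificity 80%, apparent sensitivity is (0.10 × 0.2485 + 0.20 × 0.1560)/0.4045 = 13.9%, above the true 10%.
- At specificity 95% it is 8.1%.
- Over BV 35-44%, apparent sensitivity stays at 8-14% and specificity moves by at most about 2 points.

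**Is there a matching qPCR row?**

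| Sole POCT-reference row | qPCR-reference row in SAP 5.3 |
|---|---|
| WHO any VDS vs TV/BV | Yes |
| WHO PID vs TV/BV | No; nearest is PID treated under WISH vs a CT/NG/TV/BV composite |
| WHO would-be treatment for TV/BV | Yes |
| Rwandan any VDS vs TV/BV | Not under Rwanda, but the WHO any-VDS row appears to be the same 2×2 |
| Rwandan VDS, positive score, vs TV/BV | TV only |
| Rwandan VDS, negative score, vs TV/BV | Yes |
| Asymptomatic sex worker vs TV | Yes |
| Rwandan would-be treatment for TV/BV | Yes |

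**The case against.** The strongest defence is that the SAP already contains the right analysis. Section 5.3 scores both syndromic guidelines, and TV and BV by POCT, against qPCR. Section 5.4 puts WHO, Rwandan and WISH strategies side by side against the gold standard for TV and BV. Section 5.5 counts false OSOM and pH results. The POCT blocks are headed as comparisons with WISH procedures, so the comparator is disclosed. Percent agreement is numerically the same as the planned sensitivity and specificity, and if symptoms really are about 10% sensitive for BV, the finding that they perform poorly barely changes.

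All of that stands, and it limits the point to labelling and a few rows. It does not remove it. SAP 5.4 accepts WISH procedures as reference only for syphilis and UTI, on the ground that no gold standard exists for them; for TV and BV one does. The SAP thus treats the same POCT results as truth in 5.3 and as error-prone in 5.5.

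A reader might infer that under this plan the POCT cannot lose, or that the figures are bound to favour it. The first is true only inside the POCT-reference rows; against qPCR the POCT can lose. The second is not established: under independent errors a weak rule can look slightly better than it is, and if discharge symptoms and raised pH share causes, apparent syndromic accuracy could be inflated.

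**Conclusion.** The concern holds for the POCT-reference rows of SAP 5.3 and no further. Those rows report agreement under accuracy labels. A flawless BV rule would show 61-70% and 77-83% against pH, and 68-78% and 73-81% against the combined TV/BV reference that seven of the eight rows use. The problem is mainly pH: OSOM alone would leave a perfect TV rule at about 93%/96% when TV prevalence is 15%.

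These figures assume that 71%/76% carries over to the study. That estimate was made against Nugent 7-10, not the SAP's qPCR score. They also assume BV prevalence of 35-44% and, for the composite, TV of 10-17% with independence. They are ceilings for a perfect rule, not predicted results, and the direction of bias for a real rule is open.

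Among the eight rows, two lack a full qPCR match: WHO PID against TV/BV, and Rwandan positive-score VDS against combined TV/BV. It would be tempting to add Rwandan any VDS, but as the SAP text defines it, any reported discharge, it appears to equal the WHO any-VDS row. The flowcharts are not shown, so this cannot be settled. The change should be made, but the main TV/BV comparison in 5.4 is sound as planned.

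**What to change.** In SAP 5.3:
- Report every row whose comparator includes TV and/or BV by POCT as positive and negative percent agreement, without TP/FP/FN/TN or sensitivity/specificity/PPV/NPV labels.
- Add qPCR-reference rows for WHO PID vs TV/BV and Rwandan positive-score VDS vs TV/BV and, for completeness, Rwandan any VDS vs TV/BV.
- State that all conclusions on TV and BV accuracy rest on the qPCR reference, as in 5.4, and that the protocol 4.2 endpoint is read in that sense.

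The cost is relabelling and two or three extra rows from data already held. No new samples or tests are needed. Data collection has ended, so the SAP is the place for the change.

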#### 4.2 Specific objectives and endpoints

improvement of urogenital infection care in high risk	opinions of stakeholders from
women, as evaluated in the cross-sectional study.	transcripts of workshops and IDIs.
3b.Obtain stakeholder opinions about the potential roll-	Consensus, majority and minority
out of novel vaginal microbicides and multipurpose	opinions of stakeholders from
prevention technologies for HIV and pregnancy	transcripts of workshops and IDIs.
prevention as soon as efficacious products become	
available (to prepare for future RU projects).	

#### 4.3 Sample size

The primary objective is descriptive. Formal sample size calculations were therefore not performed. We estimated to be able to see 500-700 women in one year with the funding we received from EDCTP. However, our estimate may have been conservative, in which case the sample size may be increased to up to 1,000 women. Based on prevalence data from recent RU studies in the same high risk population, if we see 500 clients (assuming that they do not opt out of any services offered), we expect to diagnose 100 cases of HIV, 35 cases of syphilis, 60 cases of NG, 75 cases of CT, 75 cases of TV, 175 cases of BV, 50 cases of vaginal candidiasis, and 115 cases of UTI.

Data for the qualitative research objectives will be gathered at two workshops with stakeholders: one to be held before initiation of the study and one after completion of the study. In addition, IDIs will be done with clinicians, programme implementers and policymakers. The number of IDIs to be held will be governed by data saturation: no new interviews will be done when they no longer generate new information. We expect to conduct approximately 10 IDIs.

#### 4.4 Randomisation and blinding

There will be no randomisation and blinding in this study.

#### 5. STUDY POPULATION

#### 5.1 Target population

Our target population is adult women living in the city of Kigali who are at high risk of HIV/STIs. In this study, high risk will be defined as having had more than one sexual partner in the last 12 months OR having been treated for an STI in the last 12 months. Women who are known to be HIV-positive and/or pregnant will not be excluded from participation. Women will be allowed to participate regardless of whether they currently have urogenital symptoms.

